Background and Rationale:	
Around 20% of the European population suffers from chronic pain. In addition to the huge emotional and physical burden of chronic pain, the financial impact on society is also enormous, currently estimated at more than €200 billion each year in Europe and \$150 billion each year in the USA. [1] However, there are many different treatment strategies for chronic pain, suggesting difficulties in effectively treating these patients. [2] In addition, a substantial number of patients do not respond to first-line treatment. [5] Medications that are frequently prescribed for pain (e.g., NSAIDs, acetaminophen, metamizole, opioids, antidepressants and antiepileptics) often have limiting side effects. [6] Opioids have the additional problem that they have a high potential for abuse and addiction. [7, 8] One possible treatment strategy, especially for therapy-resistant pain, is intravenous infusions with certain pharmacological agents, such as lidocaine and ketamine. [9] Studies have shown that treatments with lidocaine and ketamine have an immediate effect on the one hand, and can also result in longer-lasting pain relief on the other. [10-13] Lidocaine-ketamine infusions (every 4-6 weeks) have been performed at the University Hospital Basel (USB) for almost 20 years. In our pain unit, we combine the positive properties of lidocaine and ketamine by administering infusions of the two agents simultaneously. Internationally, however, safety concerns have been raised following some case studies reported serious side effects [17-19] and the death of a young mother reported in the British media after lidocaine infusion [20]. Therefore, in 2021, an international expert consensus was conducted on the efficacy and safety of intravenous lidocaine for postoperative pain. [21] The elaborated statement includes recommendations for the safe use of lidocaine infusions in the perioperative setting, such as:
 
 
- A loading dose of no more than 1.5mg/kg lidocaine given as an intravenous infusion over 10 minutes is recommended
 
- After the initial loading dose, an intravenous infusion of 1.5mg/kg/h lidocaine is recommended
 
- No more than 120mg/h of lidocaine should be infused intravenously
 

	
The dosage regimens proposed in this recommendation are clearly exceeded by the standard regime at our pain unit (i.e. 4mg/kg lidocaine over 30 minutes). For note the new consensus statement addresses perioperative use of lidocaine in acute postoperative pain, and our treatment regime is based on previous studies investigating chronic pain. [9, 22] In addition, during a previous retrospective study at our Pain Unit, no serious adverse events were registered during 2995 infusions performed, rendering it a safe procedure. [23] Nevertheless, Foo, Macfarlane et al. defined a toxic lidocaine concentration in plasma as >5µg/ml. In order to assess whether this concentration is exceeded at the USB, the aim of this pilot project is to measure the lidocaine plasma level in a limited number of patients to generate explorative data on inter- and intrapersonal stability and safety of drug plasma levels. Beyond safety issues, we are interested in dosing and effects of our treatments. In the literature, there is evidence that higher doses of ketamine are associated with greater and longer pain relief, which is also consistent with the data from our retrospective study. [23, 24] As a standard regime of our infusion therapies, we increase the ketamine dose from 0.15mg/kg at the first infusion to 0.25mg/kg at the second infusion and 0.5mg/kg at the third infusion. Therefore, another aim of this study is to investigate whether higher plasma levels of ketamine can be correlated with a better analgesic effect.

Objective(s):
	
The primary objective of this study is to measure the concentration of lidocaine in the plasma of patients at the USB after an intravenous infusion with 4mg/kg lidocaine over 30 minutes.
 
We hypothesize that lidocaine concentrations in plasma of patients at the USB are inter- and intrapersonal stable and do not exceed 5µg/ml by the end of the applied infusions.
 
The secondary objectives of this study include the prospective side effects assessment of lidocaine and ketamine as well as the measurement of plasma levels of ketamine. Further, to correlate the plasma levels with the analgesic efficacy and change in possible depressive symptoms, due to the infusions.


Outcome(s):
	
The primary endpoint of our study is the concentration of lidocaine in the plasma of patients who received an intravenous infusion with 4mg/kg lidocaine and 0.15 – 0.5mg/kg ketamine over 30 minutes at the time directly after the infusion.
 
The secondary endpoints of our study are the recorded side-effects typical for lidocaine and ketamine reported by questionnaires and patient monitoring. A further endpoint of interest is the concentration of ketamine in the plasma of patients directly after the infusion. Development of pain and mood as assessed by the Short form - McGill Pain Questionnaire (SF-MPQ) and Beck Depression Questionnaire II (BDI-II), respectively.

Study design:
	
This study is designed as monocentric observational study at the University Hospital Basel.

Inclusion / Exclusion criteria:
	
Inclusion Criteria:
 
 
- Patient is a new recipient of lidocaine-ketamine infusions
 
- Patient is 18 years of age or older
 
- Patient is able to provide Informed Consent
 
 
Exclusion Criteria:
 
 
- Contraindication to blood sampling (on arm not used for infusion)
 
- Insufficient knowledge of German language
 
- Inability to give consent
 
- Patient is under 18 years of age
 
- Contraindication to treatment with lidocaine and/or ketamine
 


Measurements and procedures:
	
Standard procedure of lidocaine/ketamine infusions at USB
 
Patients with therapy refractory chronic pain are scheduled for Infusion therapies on a four-week interval basis, by their treating pain physician. Before each infusion, a brief medical history interview takes place, during which compliance with the fasting time (6 hours for solid food, 2 hours for clear liquids) in particular is queried. Subsequently, installation of monitoring (10-minute blood pressure measurement, continuous 5-lead ECG, and continuous SPO2 measurement) and placement of venous access. Lidocaine and ketamine are infused over a 30-minute period (detailed dosing schedules are provided in the protocol). After infusion, patients are monitored for at least another half hour, discharged in company, and instructed not to operate heavy machinery or motor vehicles for at least 24 hours. Over the first three infusions the Ketamine dose is adjusted up to 0.5mg/kg/bw, the Lidocaine dose is stable at 4mg/kg/bw during the infusions. Beyond the third infusion dose adjustments are only made if needed (c.f. side-effects)
 
Study procedures
 
Recruitment and consent to participate in the study will take place in the consultation prior to the first infusion. (c.f. 3.2) During the infusion, the patients' vital signs will be monitored as usual (10-minute blood pressure measurement, continuous SPO2 and 5-lead ECG are recorded, c.f. 3.3.2). As a part of this study, at the end of the first, second and third infusion, side effects will be screened using customized questionnaires. (c.f. eCRF forms document). In addition, blood will be collected during each of the first three infusion appointments. The blood collection itself will take place within 3 minutes after termination of the infusion, as we assume the highest plasma levels at that point in time. [25, 26] For blood collection we will use a Butterfly cannula (BBraun Venofix® Safety 23G, PZN 08839883, B. Braun Melsungen AG) which will be inserted on the "non-infusion arm" and two green 7.5ml Lithium-Heparin monovettes (S-Monovette® Lithium-Heparin, liquid, preparation: lithium heparin, liquid, 7.5 ml, membrane screw cap, closure green, color code ISO, (LxØ) without closure: 92 x 15 mm, with paper label, label/printing: green Sarstedt AG & Co. KG, Nümbrecht).
 
Patients will complete the Short form - McGill Pain Questionnaire (with additional recording of pain on the numeric rating scale (NRS) from 0 (no pain at all) to 10 (worst pain imaginable)) and Beck Depression Questionnaire directly prior to the first three infusions. The SF – MPQ is a validated instrument for measures of clinical pain that capture its sensory, affective and other qualitative components. [27] The BDI-II provides a validated psychological test procedure that assesses the severity of


depressive symptoms in adolescents 13 years of age and older and adults. [28]

In addition, these questionnaires will also be completed at the time points 7 days after, and 14 days after the first, second and third Infusion. The participants will receive a link by e-mail so that they can fill in the questionnaires online. According to the license agreement, the BDI-II will be filled out in paper form and the results will be subsequently transferred to REDCap. If desired by the participant, these questionnaires can also be completed during a telephone survey conducted by the study staff. The surveys will be conducted with REDCap. After the third infusion, this online questioning will take place additionally after 28 days (c.f. Appendix 1). After this questioning, the study ends for the participants.

### **Investigated variables**

#### **Demographic**

Variable: Age

Categories: Age at beginning of therapy (recorded in years)

Variable: Gender

Categories: female / male / diverse

Variable: Nationality

Categories: Recorded as free text

Variable: Diagnosis that led to the indication for lidocaine/ketamine infusion

Categories: Main pain-related diagnosis coded with ICD11, free text

Variable: Dosage

Categories: Weight (recorded in kg) / Height (recorded in cm) / Dosage of lidocaine (recorded in mg) / Dosage of ketamine (recorded in mg)

#### **Effects and Side effects**

Variable: Depressive Symptoms

Categories: Recorded by BDI-II at the beginning of the infusion, 7 days after and 14 days after

Variable: Pain

Categories: Recorded by SF-MPQ-2 at the beginning of the infusion, 7 days after and 14 days after, and by NRS (Number from 0 to 10) at the beginning of the infusion, 7 days after and 14 days after

Variable: Vital signs

Categories: blood pressure (recorded in mmHg) / heart rate (recorded in bpm) / saturation of oxygen under infusion (recorded as percentage) / Respiratory rate (recorded in breaths per minute), recorded at the start of the infusion and subsequently during a period of 60 minutes

Variable: ECG

Categories: Heart rate (recorded in bpm), regular sinus rhythm (recorded as yes or no), PQ interval (recorded in ms), QRS-complex (recorded in ms), ST segment (recorded as conspicuous/inconspicuous), T wave (recorded as conspicuous/inconspicuous), QTc (recorded in ms), Extrasystolies (recorded as number), other anomalies (recorded as free text) at start of infusion and at the end of infusion (minute 30)

Variable: Side effects at end of infusion (patient recorded)

	
Categories: Injection site pain, dysphoria, euphoria, nervousness, anxiety, dyspnea, nausea, hypersalivation, nightmares, hallucinations, visual disturbances, tinnitus, hyperacusis, paresthesias, numbness, dizziness (recorded as present/absent).
 
Variable: Side effects at end of infusion (patient observation by physician, monitoring)
 
Categories: Exanthema, redness injection site, vomiting, tremor, dysarthria, nystagmus, convulsions, dissociation, disorientation, restlessness, agitation (recorded as present/absent)
 
Variable: Medication plasma levels
 
Categories: Lidocaine and ketamine plasma levels are recorded specified in mg/l at the end of infusions
 
Laboratory Analysis
 
Samples were analyzed on a Thermo Scientific™ Orbitrap Exploris™ 240 Mass Spectrometer coupled to reversed phase liquid chromatography with an LLOQ of 0.1 µmol/L for lidocaine and 0.1 mg/L for ketamine. The methods were fully validated according to EMA guideline.

Number of Participants with Rationale:	A total of max. 15 patients (10 + Drop-out of 50%) will be included.
Study Duration:	In total, we expect a study duration of 7 months. Study duration for each individual participant will be 12 weeks.
Study Schedule:	First-Participant-In: 06/2023 Last-Participant-Out: 12/2023

Statistical Considerations:	
Patients characteristics regarding to age, gender, pharmacological treatment, medical diagnosis will be analyzed exploratively/ descriptively.
 
Primary outcome:
 
The primary outcome (Lidocaine plasma level) of our study is explorative and not comparative, therefore, no H0 or H1 are formulated no power analysis is performed and only descriptive/ explorative statistics are reported.
 
We plan to include 10 patients with complete data sets, meaning, full data of three infusions with stable dose of lidocaine (4mg/kg/BW) and escalating dose of ketamine (0.15 – 0.5mg/kg/BW). This corresponds to thirty measures of lidocaine plasma concentrations at a dose of 4mg/kg/BW). Patients without full data sets will be replaced but data from patients with preliminary study termination will be reported in the final protocol.
 
Secondary outcomes:
 
 
1. Ketamine plasma levels are assessed according to lidocaine levels.
 
2. H0: dose escalation of ketamine has no effect on pain (outcome measure: SF-MPQ-2) and mood (outcome measure: BDI-II. H1: we hypothesize that ketamine dose has an effect on both outcome measures. For repeated measurements, an ANOVA will be separately calculated for outcome measures of pain and mood as dependent variable. This analysis will be performed separately for intermediate (one and two weeks) and
 

	
long term effects (four weeks). For comparative outcomes a level of significance of 0.05 will be used. In case of multiple testing a correction factor (in case of ANOVA: Bonferroni) for multiple testing is applied.
 
3. Side effects during treatment will be primary analyzed descriptively.
 
4. Multiple exploratory linear regressions will be calculated to evaluate the impact of dose and plasma levels of lidocaine and ketamine on pain and mood as well as occurrence of side-effects.
 
SPSS Version 25 will be used for data analyzation and graph pad PRISM Version 9 for data visualization. The investigators, [name] and [name], will perform all analysis steps. If needed, statistical guidance will be applied by statisticians of the Clinical Trial Unit (CTU) of the USB.
 
Handling of missing data:
 
Dropouts will be replaced. We do not plan data imputation.

GCP Statement:	
This study will be conducted in compliance with the protocol, the current version of the Declaration of Helsinki, the ICH-GCP or ISO EN 14155 (as far as applicable) as well as all national legal and regulatory requirements.

133  
134

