#### 400 **Secondary outcomes:**

401 1. Ketamine plasma levels are assessed according to lidocaine levels.

402

403 2. H0: dose escalation of ketamine has no effect on pain (outcome measure: SF-MPQ-2) and  
404 mood (outcome measure: BDI-II. H1: we hypothesize that ketamine dose has an effect on both  
405 outcome measures. For repeated measurements, an ANOVA will be separately calculated for  
406 outcome measures of pain and mood as dependent variable. This analysis will be performed  
407 separately for intermediate (one and two weeks) and long term effects (four weeks). For  
408 comparative outcomes a level of significance of 0.05 will be used. In case of multiple testing, a  
409 correction factor (in case of ANOVA: Bonferroni) for multiple testing is applied.

410

411 3. Side effects during treatment will be primary analyzed descriptively.

412

413 4. Multiple exploratory linear regressions will be calculated to evaluate the impact of dose and  
414 plasma levels of lidocaine and ketamine on pain and mood as well as occurrence of side-effects.

415

416 SPSS Version 25 will be used for data analyzation and graph pad PRISM Version 9 for data  
417 visualization. The investigators, [name] and [name], will perform all analysis  
418 steps. If needed, statistical guidance will be applied by statisticians of the Clinical Trial Unit (CTU)  
419 of the USB.

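### Secondary item 2 corrects for multiple testing with Bonferroni, which is valid, but Holm holds the same 0.05 family-wise error and never rejects less

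*Protocol*

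**What the plan says.** The text is in the synopsis under Statistical Considerations and, almost word for word, in section 4.1 under Secondary outcomes, item 2.

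- Null hypothesis: "H0: dose escalation of ketamine has no effect on pain (outcome measure: SF-MPQ-2) and mood (outcome measure: BDI-II".
- Alternative: "H1: we hypothesize that ketamine dose has an effect on both outcome measures".
- Unit of testing: "an ANOVA will be separately calculated for outcome measures of pain and mood as dependent variable".
- Time horizons: "This analysis will be performed separately for intermediate (one and two weeks) and" long-term effects at four weeks.
- Level: "For comparative outcomes a level of significance of 0.05 will be used".
- Correction: "In case of multiple testing a correction factor (in case of ANOVA: Bonferroni) for multiple testing is applied".
- Sample: "We plan to include 10 patients with complete data sets, meaning, full data of three infusions".

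No effect size or power is given for item 2. The text does not say which tests the correction covers.

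**The concern.** Item 2 is the only place where the protocol sets out formal hypotheses, so it is where a multiplicity procedure has work to do. Single-step Bonferroni compares every p-value in the family with 0.05/m. Holm compares only the smallest with that threshold and relaxes it for each later one. Bonferroni therefore gives up some rejections that the same error guarantee would allow.

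Two matters of wording lie alongside this. The corrected family is not named, so the per-test level cannot be read off the text. The hypotheses are also written as one joint pair, although the ANOVAs are run outcome by outcome. What is at stake is some power for the second and later rejections in a secondary analysis. The primary outcome, lidocaine plasma level, is descriptive and is not affected.

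**Working it through.** **Inputs from the protocol.** Level 0.05, 2 outcomes (SF-MPQ-2, BDI-II), 2 horizons (intermediate, long term), 10 complete patients, 3 infusions.

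**Step 1: does Bonferroni do what the plan asks?** The bound on family-wise error is m × (0.05/m) = 0.05 for any m. If the tests are independent, it is 1 − (1 − 0.05/m)^m.

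| Family | m | Per-test level | Error with Bonferroni | Error uncorrected, 1 − 0.95^m |
|---|---|---|---|---|
| 2 outcomes | 2 | 0.025 | 0.0494 | 0.0975 |
| 2 outcomes × 2 horizons | 4 | 0.0125 | 0.0491 | 0.185 |
| 2 outcomes × weeks 1, 2 and 4 | 6 | 0.0083 | 0.0490 | 0.265 |

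The stated 0.05 is met in each case. If the correction instead means the 3 pairwise infusion comparisons within one ANOVA, the per-test level is 0.05/3 = 0.0167.

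**Step 2: Holm against Bonferroni.** Sort the p-values from smallest to largest. Holm compares them in turn with 0.05/m, 0.05/(m − 1), and so on up to 0.05, and stops at the first failure. For m = 4:

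- Bonferroni: 0.0125, 0.0125, 0.0125, 0.0125.
- Holm: 0.0125, 0.0167, 0.025, 0.05.

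No Holm threshold is below its Bonferroni counterpart, so every Bonferroni rejection is also a Holm rejection. The first threshold is the same, so the chance of at least one rejection is identical. Holm can help only from the second rejection on.

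**Step 3: size of the gain.** The protocol gives no effect size and no correlation, so both are assumed. The model is n = 10, four two-sided paired t-tests standing in for the repeated-measures tests, and correlation 0.5. Effects are in SD units. Results are simulated.

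| Assumed effect | Bonferroni, per test | Holm, two of four real | Holm, all four real |
|---|---|---|---|
| 0.3 | about 4.5% | about 5% | about 5% |
| 0.5 | 12% | 13% | 15% |
| 0.8 | about 35% | 37% | 43% |
| 1.0 | about 55% | 58% | 67% |

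With only the two outcomes as the family and a real effect of 0.8 SD on both, the chance of rejecting both rises from 0.226 to 0.361 at correlation 0, and from 0.292 to 0.422 at correlation 0.5. The chance of at least one rejection stays at 0.721 and 0.650 respectively.

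**Step 4: error rate under Holm.** With two tests and both nulls true, the two procedures give the same simulated error: 0.049 at correlation 0 and 0.047 at correlation 0.5. With an effect of 0.8 SD on one outcome only and correlation 0, the error on the other is 0.025 under Bonferroni and 0.037 under Holm. Both are below 0.05.

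**The case against.** The strongest reply is that nothing here is wrong. Bonferroni holds 0.05, this is a secondary analysis in a pilot that claims no power, and preferring Holm is a design choice. That stands: this is an improvement and not the correction of an error.

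The size of the gain is also open to challenge. Power of 80% per test with 10 patients needs an effect of about 1 SD, so power figures that start from 80% are optimistic. At 0.3 to 0.5 SD the gain is at most about 3 percentage points. With two real effects of four it is 1 to 3 points from 0.5 SD upwards, and smaller at 0.3 SD. This stands too, and is why a range is shown.

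The four-test family is one reading. The parenthesis about ANOVA may refer to pairwise comparisons between infusions. The text leaves this open, but Holm's advantage holds for either family.

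Bonferroni has one advantage that stands: it gives simple simultaneous confidence intervals that match its tests, and Holm does not.

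Two stronger readings are tempting, and the document supports neither.

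- A reader might infer that a result on one outcome only has no defined conclusion, because no effect on pain and mood is not the complement of an effect on both. Read literally, the joint pair does leave that case out. But the next sentence gives each outcome its own ANOVA, and no joint decision rule appears anywhere. A significant pain result rejects the null for pain and leaves the null for mood standing. This is loose wording and changes no number. Nor does the wording make success on both outcomes a requirement that would remove the need for correction.
- A reader might infer an 18.5% family-wise error. That is the rate for four independent uncorrected tests. The plan does correct, so the figure does not apply if the correction covers those four tests.

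**Conclusion.** The point holds as a low-cost improvement. Holm keeps the 0.05 family-wise error of the planned Bonferroni correction and is never less powerful. In the four-test family the per-test gain runs from under 1 point at 0.3 SD to about 12 points at 1.0 SD with all four effects real. It does nothing for the chance of finding any effect at all. Validity and dominance rest on no assumption about effects or correlation. The sizes do: they assume a paired-t stand-in, correlation 0.5, 10 patients, equal effects and a four-test family. The unnamed family and the joint H0/H1 wording are matters of clarity.

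**What to change.** In the synopsis and section 4.1, Secondary outcomes, item 2:

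1. Replace Bonferroni by Holm (Bonferroni-Holm).
2. Name the corrected family: for example, the four omnibus p-values (2 outcomes × 2 horizons), or the pairwise infusion comparisons within each ANOVA.
3. As an editorial clarification, write one H0/H1 pair for SF-MPQ-2 and one for BDI-II.
4. Report unadjusted or Bonferroni confidence intervals alongside, labelled as such, because Holm has no simple matching simultaneous intervals.

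The cost is a few sentences in two places, with no extra patients or data. The only statistical cost is that some intervals may not agree exactly with the Holm decisions.

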## 135 1 BACKGROUND AND PROJECT RATIONALE

136 Around 20% of the European population suffers from chronic pain. In addition to the huge  
137 emotional and physical burden of chronic pain the financial impact on society is also enormous,  
138 currently estimated at more than €200 billion each year in Europe and \$150 billion each year in  
139 the USA. [1] Moreover, chronic pain is the most common cause of long-term disability in middle-  
140 aged people. [2] Chronic pain is complex and the pathomechanisms behind it are still not fully  
141 understood. Nevertheless, it is increasingly regarded not only as a symptom, but as a disease in  
142 its own right. This is also visible in the fact that chronic pain can be coded independently for the  
143 first time in ICD 11. [3] In recent years, clinical research has shown that chronic pain can occur  
144 independently of disease or tissue damage due to increased sensitization of the central or  
145 peripheral nervous system. If chronic pain is inadequately treated, it leads to multidimensional  
146 adverse effects: Impairments in daily activities and work ability, general health, and social life. [4]  
147 However, there are many different treatment strategies for chronic pain, suggesting difficulties in  
148 effectively treating these patients. [2] In addition, a substantial number of patients do not respond  
149 to first-line treatment. [5] Medications that are frequently prescribed for pain (e.g., NSAIDs,  
150 acetaminophen, metamizole, opioids, antidepressants and antiepileptics) often have limiting side  
151 effects. [6] Opioids have the additional problem that they have a high potential for abuse and  
152 addiction. [7, 8]

153 One possible treatment strategy, especially for therapy-resistant pain, is intravenous infusions  
154 with certain pharmacological agents, such as lidocaine and ketamine [9] Studies have shown that  
155 treatments with lidocaine and ketamine have an immediate effect on the one hand, and can also  
156 result in longer-lasting pain relief on the other. [10-13] Ketamine is also interesting for pain therapy  
157 due to its antidepressant effect [14, 15] since chronic pain is often accompanied by depressive  
158 symptoms. [16]

159 Lidocaine-ketamine infusions (every 4-6 weeks) have been performed at the University Hospital  
160 Basel (USB) for almost 20 years. In our pain unit, we combine the positive properties of lidocaine  
161 and ketamine by administering infusions of the two agents simultaneously. This allows us to  
162 achieve good clinical results in patients who are non-responders to first- or second-line therapy.

163 Internationally, however, safety concerns have been raised following some case studies reported  
164 serious side effects [17-19] and the death of a young mother reported in the British media after  
165 lidocaine infusion. [20] Therefore, in 2021, an international expert consensus was conducted on  
166 the efficacy and safety of intravenous lidocaine for postoperative pain. [21] The elaborated  
167 statement includes recommendations for the safe use of lidocaine infusions in the perioperative  
168 setting, such as:

- 169
- 170 - A loading dose of no more than 1.5mg/kg lidocaine given as an intravenous infusion over 10  
171 minutes is recommended
  - 172 - After the initial loading dose, an intravenous infusion of 1.5mg/kg/h lidocaine is recommended
  - 173 - No more than 120mg/h of lidocaine should be infused intravenously
  - 174 - For the dose calculation, the ideal body weight should be used
- 175

176 The dosage regimens proposed in this recommendation are clearly exceeded by the standard  
177 regime at our pain unit (i.e. 4mg/kg lidocaine over 30 minutes). For note the new consensus  
178 statement addresses perioperative use of lidocaine in acute postoperative pain, and our treatment  
179 regime is based on previous studies investigating chronic pain. [9, 22] In addition, during a  
180 previous retrospective study at our Pain Unit, no serious adverse events were registered during  
181 2995 infusions performed, rendering it a safe procedure. [23] Nevertheless, Foo, Macfarlane et  
182 al. defined a toxic lidocaine concentration in plasma as  $>5\mu\text{g/ml}$ . In order to assess whether this  
183 concentration is exceeded at the USB, the aim of this pilot project is to measure the lidocaine  
184 plasma level in a limited number of patients to generate explorative data on inter- and  
185 intrapersonal stability and safety of drug plasma levels.

186 Beyond safety issues, we are interested in dosing and effects of our treatments. In the literature,  
187 there is evidence that higher doses of ketamine are associated with greater and longer pain relief,  
188 which is also consistent with the data from our retrospective study. [23, 24] As a standard regime  
189 of our infusion therapies, we increase the ketamine dose from 0.15mg/kg at the first infusion to  
190 0.25mg/kg at the second infusion and 0.5mg/kg at the third infusion. In cases where patients  
191 already experiencing sufficient analgesic effect and/or improvement in quality of life after the 1st  
192 or 2nd infusion or if side effects are not tolerated, no further increase of ketamine dosage is made.  
193 Therefore, another aim of this study is to investigate whether higher plasma levels of ketamine  
194 can be correlated with a better analgesic effect.

195

